### **Background**

Endocuff Vision is a disposable device that fits over the end of a colonoscope. A row of flexible fingers extending from the device is used to flatten and deflect haustral folds during colonoscope withdrawal, which has been shown to improve adenoma detection, as well as detection of serrated polyps.

The Amplifeye device is a less expensive competitive device of similar design to the Endocuff Vision. Both Endocuff Vision and Amplify devices are FDA approved.

In this study, we propose to compare the Endocuff Vision and the Medivators AmplifEYE device in a randomized controlled trial using adenomas per colonoscopy as the primary endpoint. If the adenomas per colonoscopy with the Medivators device is shown to be non-inferior to Endocuff Vision, then the less expensive Medivators device could be used in place of the Endocuff Vision.

Both devices have been considered to be safe for use in clinical practice. Clinical trial evidence showing benefits of the Amplifeye device compared to no device have not been demonstrated.

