## **Objectives**

The *primary endpoint* will be the number of conventional adenomas per colonoscopy of the Endocuff Vision Colonoscopy compared to that of the AmplifEYE colonoscopy. Adenomas per colonoscopy is calculated as the total number of adenomas detected divided by the total number of colonoscopies.

*Secondary endpoints* will include the following:

- Adenoma detection rate (calculated as the percentage of colonoscopies in which at least one adenoma was detected)
- Complications encountered during procedure (i.e., mucosal trauma, perforation, or gastrointestinal bleeding)
- Ability to pass device through the sigmoid colon (success rate of the device passing the sigmoid colon of the large intestine)
- Polyp detection rate
- Polyps per colonoscopy
- Exam times
  - *Total procedure time* – Total time of procedure from insertion to withdrawal
  - *Cecal insertion time* – Time of colonoscope insertion (from insertion into the rectum to the cecum)
  - *Overall withdrawal time* – Total time of colonoscope withdrawal (from cecum until the scope is withdrawn from the rectum)
  - *Inspection time* – Inspection time is defined the same as withdrawal time, but with the clock stopped for washing, suctioning, and polyp removal (or other non-inspection related activities)
- Cecal intubation rate (the success rate of reaching the cecum)
- Detection of serrated and flat lesions
- Retroflexion completion rate (ability to complete retroflexion)

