### **Statistical Analysis & Sample Size**

The primary endpoint will be the number of conventional adenomas per colonoscopy. Based on previous data (1) we estimate that the Endocuff Vision will result in an APC of 2.3. We consider that a clinically acceptable ADR for the Medivators device would be within 20% of this value or 1.84. To demonstrate non-inferiority, a sample size of 588 patients should be randomized.

With a sample size of 294 patients per group, the study will have 80% power to detect non-inferiority between the two groups, assuming tests using a one-sided two-sample t-test, a coefficient of variation 1.5 for both groups, and a noninferiority margin of 20%.

The number of conventional adenomas per colonoscopy will be compared between the Endocuff Vision and AmplifEYE groups using a two-sample t-test on the log-transformed adenoma count. Similar analyses will be performed for the number of polyps, serrated lesions, and flat lesions per colonoscopy. Two-sample t-tests (or Wilcoxon Rank Sum tests if non-normally distributed) will be used for comparisons of exam times. Chi-square tests will be used to compare the groups for differences in adenoma, polyp, serrated lesion, and flat lesion detection rates; complications; ability to pass the device through the sigmoid colon; and cecal intubation rate. A 5% significance level will be used for all tests.

In order to account for patient withdrawals, 20 additional patients will be enrolled in the study to ensure sufficient data will be included in the analysis.

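### The primary t-test on log-transformed adenoma counts cannot test the stated 20% margin, which is set on mean adenomas per colonoscopy, because zero counts are expected

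*Combined protocol and SAP*

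**What the plan says.** All references are to the combined protocol and SAP.

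- **Aim.** Background makes use of the cheaper device conditional on a non-inferiority result: "If the adenomas per colonoscopy with the Medivators device is shown to be non-inferior to Endocuff Vision".
- **Endpoint.** Objectives defines the measure: "Adenomas per colonoscopy is calculated as the total number of adenomas detected divided by the total number of colonoscopies". That is an arithmetic mean per patient, and patients without adenomas count in the denominator.
- **Margin.** Statistical Analysis & Sample Size first gives the reference value, "we estimate that the Endocuff Vision will result in an APC of 2.3", and then an acceptable value for the comparator that "would be within 20% of this value or 1.84".
- **Power.** The same section gives 80% power with 294 per group, "assuming tests using a one-sided two-sample t-test, a coefficient of variation 1.5 for both groups, and a noninferiority margin of 20" per cent.
- **Analysis.** The next paragraph says the count "will be compared between the Endocuff Vision and AmplifEYE groups using a two-sample t-test on the log-transformed adenoma count", and adds "A 5% significance level will be used for all tests".

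The plan says nothing about how a count of zero enters the log transformation, or which ratio is to be held against the 20% margin.

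**The concern.** The margin and the test are on different scales. A 20% loss in APC is a ratio of arithmetic means of 0.80. A t-test on log counts compares means of logs, which after back-transformation is a ratio of geometric means. The two ratios agree only under particular conditions, and one of those is that every count is positive.

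That condition will not hold here. Objectives lists a secondary detection rate, the share of examinations with one or more adenomas, and this has a purpose only if some examinations find none. For those patients the planned outcome variable does not exist, so the analyst must choose a workaround. The choice decides what is being compared with 0.80, and so decides the trial's one main conclusion. The error runs in the unsafe direction: a device that does lose 20% of APC looks closer to its comparator than it is.

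**Working it through.** **1. Reproduce the plan's sample size.** Inputs from Statistical Analysis & Sample Size: CV 1.5 in both groups, a 20% margin, a one-sided t-test, the 5% level and 294 per group. The assumed true ratio is 1.

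- Log-scale SD = sqrt(ln(1 + 1.5²)) = 1.0857
- Margin = -ln 0.80 = 0.2231
- SE = 1.0857 × sqrt(2/294) = 0.0895, with 586 degrees of freedom
- Noncentral-t power at one-sided 5% = 80.07% (79.96% at 293 per group)

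So 294 is correct, on the assumption that counts are lognormal and therefore never zero. Under that assumption, with a common CV, the ratio of geometric means equals the ratio of arithmetic means, and 0.80 has one meaning.

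**2. Locate the margin.** 0.80 × 2.3 = 1.84. The limit is a mean APC, consistent with the definition in Objectives.

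**3. See what the workarounds do.**

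- *Add 1 before taking logs.* The added constant pulls the ratio towards 1. As a rough guide, (1.84 + 1)/(2.3 + 1) = 2.84/3.30 = 0.86. A true 20% loss already sits above 0.80 on the shifted scale.
- *Drop zeros.* Only patients with at least one adenoma are compared. Any loss that shows up as more patients with none leaves the comparison, and the groups compared are no longer the randomised groups.

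**4. Size the effect.** The documents give no share of zeros and no count distribution, so two illustrative models were used, each matched to mean 2.3 and CV 1.5 (SD 3.45, variance 11.9):

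- negative binomial with variance m + 1.815m² (check: 2.3 + 1.815 × 5.29 = 11.9), about 40% zeros
- Poisson-lognormal with log-variance 1.035, about 30% zeros

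There were 20,000 simulated trials of 294 per group. The comparator's mean was 1.84, so its true APC ratio was exactly 0.80. The rule was that the lower limit of a two-sided 90% CI exceeds 0.80. Ranges cover both models, with either a common dispersion or CV 1.5 in both groups.

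| Quantity compared with 0.80 | Trials passing at true APC ratio 0.80 |
|---|---|
| Ratio of mean APC | 4.9-5.5% |
| Exponentiated difference in mean log(count + 1) | 53-61% |
| Exponentiated difference in mean log count, zeros dropped | roughly 30-44% |

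The nominal figure is 5%.

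**5. Power for the quantity the margin refers to.** True ratio 1, CV 1.5, 294 per group:

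- SE of the log ratio of means = 1.5 × sqrt(2/294) = 0.1237
- Power ≈ Φ(0.2231/0.1237 - 1.645) = Φ(0.159) = 0.563
- As a linear contrast, mean(A) - 0.8 × mean(E): SE relative to the mean = 1.5 × sqrt(1.64/294) = 0.112, which also gives about 0.56
- Simulated power: 56-57% (negative binomial) and 57-58% (Poisson-lognormal)
- CV at which 294 per group gives 80%: 0.2231/(2.4865 × sqrt(2/294)) = 1.09, where 2.4865 = 1.645 + 0.842

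**The case against.** The best reply is that the plan is coherent on its own inputs. Under the lognormal model behind the sample size, with one CV for both groups, geometric and arithmetic ratios coincide and the log-scale t-test addresses the 20% margin. The plan never mentions adding 1 or dropping zeros, and the 30-40% share of zeros comes from the review, not the documents. All of this is true. It protects the figure of 294 as a calculation. It does not protect the analysis, because the endpoint is a count that can be zero and the log of zero is undefined. Some departure from the written method is unavoidable, and neither of the common departures keeps 0.80 as a 20% loss in APC.

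Three stronger readings are tempting, and the documents do not support them.

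- *The plan lacks a non-inferiority test, or would treat a non-significant difference as non-inferiority.* The analysis paragraph does not repeat the margin or the sidedness, but the power paragraph just before it states both. Nothing says that non-significance would count as success.
- *The 5% might be meant as two-sided for the margin test.* The power paragraph says one-sided, and 294 reproduces at one-sided 5%. Restating this beside the analysis would be a clarification only.
- *The margin is on the detection rate.* The threshold sentence, "We consider that a clinically acceptable ADR for the Medivators device would be within 20% of this value or 1.84", uses that label, but the value is 0.8 × 2.3, an APC. It is a labelling slip.

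**Conclusion.** The concern holds for the analysis method. As written, the primary test cannot be computed for patients with no adenoma, and the common ways round this test something other than the stated margin. That conclusion needs only the definition of APC, the 1.84 against 2.3 threshold and the presence of zeros.

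The size depends on assumptions. With mean 2.3, CV 1.5 and 30-40% zeros, a device at the edge of unacceptability passes in roughly 30-60% of trials instead of 5%. A different share of zeros or a different distribution would change the figure.

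The sample size contains no arithmetic error. Its 80% power belongs to a zero-free log-scale comparison. For the ratio of mean APC at CV 1.5, power is about 56-58%.

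**What to change.** Replace the log-count t-test for the primary endpoint in Statistical Analysis & Sample Size with wording such as:

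> The AmplifEYE/Endocuff Vision ratio of mean adenomas per colonoscopy will be estimated with all zero counts included, using a log-link count model with robust standard errors. AmplifEYE will be declared non-inferior only if the lower limit of the two-sided 90% confidence interval (one-sided 5%) for this ratio exceeds 0.80.

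Restate the power for this ratio: about 56-58% at CV 1.5 with 294 per group, and 80% only if a CV of about 1.09 can be justified. In the threshold sentence, change ADR to APC as a label correction.

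The cost is a few sentences and a revised power statement. Data collection is unchanged. The drawback is that the stated power becomes less favourable, and the sponsor must either support a smaller CV or accept the lower figure. Raising the sample size is not part of this fix.

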### **Methods**

This will be a randomized controlled trial in patients age 40 and older undergoing colonoscopy for screening, surveillance, or diagnostic reasons. They will be randomized to one of two arms, i.e. High Definition colonoscopy with Endocuff Vision or High Definition colonoscopy with AmplifEYE.

A member of the research team will approach a potential subject to discuss participation in the study, including background of the proposed study, inclusion and exclusion criteria, benefits and risks of the procedures and follow-up. Prior to study enrollment, a subject must sign an informed consent document, which details the essential aspects of this study. The informed consent document will have prior approval of the study site's Institutional Review Board (IRB). Failure to obtain informed consent renders the subject ineligible for the study.

Data collected will include the type of scope used (adult versus pediatric); age; gender; indication; history of prior abdominal surgery and type; and identification of diverticulosis classified as mild, moderate, or severe. Additionally, exam time including insertion time, total procedure time, overall withdrawal time, and inspection time (withdrawal time minus anytime suctioning, cleaning, and diagnostic biopsy or therapeutic procedure) as well as retroflexion completion rates (ability to complete retroflexion) will be recorded. For each polyp, we will record the location, size, shape, and pathology. The bowel preparation will be evaluated and graded according to the Boston Bowel Preparation Scale. Complications including any mucosal trauma from the high definition colonoscope with Endocuff Vision or with AmplifEYE, perforation or gastrointestinal bleeding (requiring intervention) will be recorded.

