### **Inclusion criteria**

- Undergoing colonoscopy for screening, surveillance, or diagnostic reasons
- Ability to provide informed consent
- 40 years and older

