## **Randomization**

Once a patient has been screened to ensure the inclusion and exclusion criteria have been met and has provided consent for participation in the study, the subject will be randomized in a 1:1 ratio. Randomization outcomes include the Endocuff Vision Colonoscopy or the AmplifEYE Colonoscopy.

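### Prespecifying age, gender and indication as covariates in the primary comparison would be a cheap, minor improvement; leaving them out costs a little precision but causes no bias.

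*Combined protocol and SAP*

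**What the plan says.** All references are to the combined protocol and SAP.

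- **Primary analysis** (Statistical Analysis & Sample Size): the adenoma count is to be "compared between the Endocuff Vision and AmplifEYE groups using a two-sample t-test on the log-transformed adenoma count". No covariate is named, either for the primary comparison or for a sensitivity analysis.
- **Limit** (same section): Endocuff Vision is expected to give 2.3 adenomas per colonoscopy, and an acceptable result for the other device "would be within 20% of this value or 1.84". That sentence calls the quantity an ADR, but 2.3 is introduced as an APC and is read as one here.
- **Sample size** (same section): 294 per group for 80% power with a one-sided t-test, assuming "a coefficient of variation 1.5 for both groups, and a noninferiority margin of 20" percent.
- **Endpoint** (Objectives): "Adenomas per colonoscopy is calculated as the total number of adenomas detected divided by the total number of colonoscopies". The adenoma detection rate is "calculated as the percentage of colonoscopies in which at least one adenoma was detected", so colonoscopies with a count of zero are expected.
- **Baseline data** (Methods): "Data collected will include the type of scope used (adult versus pediatric); age; gender; indication".
- **Population** (Inclusion criteria): "Undergoing colonoscopy for screening, surveillance, or diagnostic reasons", from age 40 upward.
- **Allocation** (Randomization): "the subject will be randomized in a 1:1 ratio". No stratification factor is stated.

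**The concern.** Neither the design nor the analysis uses baseline information. The trial enrols patients with three kinds of indication over a wide age range. If adenoma counts differ with age, gender or indication, that variation stays in the error term and widens the confidence interval.

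Non-inferiority is decided by one confidence bound against a ratio of 0.80, so precision bears directly on the conclusion. The three variables cost nothing more to collect. The timing matters because an adjusted result whose covariates were picked after the data were seen would carry little weight. With no stratification stated, a chance imbalance in indication or age would also have no prespecified handling.

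**Working it through.** **1. The plan's own figure.** Inputs from Statistical Analysis & Sample Size: coefficient of variation (CV) 1.5, margin 20%, one-sided test, 5% level, 80% power. On the lognormal scale:

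- σ² = ln(1 + 1.5²) = 1.1787, so σ = 1.0857
- margin = −ln(0.80) = 0.2231
- n per arm = 2(1.645 + 0.842)² × 1.1787 / 0.2231² ≈ 293; the exact noncentral-t calculation gives 294, with power 80.1%

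The stated 294 is reproduced. It contains no allowance for covariates.

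**2. The scale on which to measure the gain.** The limit is 1.84/2.3 = 0.80, a ratio of arithmetic means, and zeros are expected. As an illustration, assume a negative binomial count with mean 2.3 and CV 1.5:

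- variance = (1.5 × 2.3)² = 11.90
- dispersion = (11.90 − 2.3)/2.3² = 1.815
- P(0) = (1 + 1.815 × 2.3)^(−1/1.815) = 40.4%

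Since the log of zero is undefined, the comparison with and without covariates is made within a log-link model for the ratio of means.

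**3. Formula.** SE of the log ratio = 1.5 × √(2(1 − R²)/294). Power is noncentral-t, one-sided 5%, devices truly equal, with 586 degrees of freedom unadjusted and 582 adjusted (age 1, gender 1, indication 2). R² is the share of count variance explained. It is an assumption, because the documents give no value.

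| Assumed R² | SE | Power | Gain (points) | Equivalent n per arm, 294/(1 − R²) |
|---|---|---|---|---|
| 0 | 0.1237 | 56.2% | – | 294 |
| 2% | 0.1225 | 56.9% | 0.7 | 300 |
| 5% | 0.1206 | 58.1% | 1.9 | 309 |
| 10% | 0.1174 | 60.0% | 3.8 | 327 |
| 20% | 0.1107 | 64.4% | 8.2 | 368 |

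**4. Simulation.** 10,000 trials per setting; negative binomial counts with the marginal CV held at 1.5; continuous age, gender 50/50, indication 40/40/20 (all assumed); Poisson log-link mean with robust variance. Each cell gives unadjusted / adjusted.

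| Assumed R² | Power at equal devices | False non-inferiority at ratio 0.80 |
|---|---|---|
| 0 | 56.5 / 56.5% | 5.3 / 5.3% |
| 2% | 57.0 / 57.2% | 4.7 / 4.7% |
| 5% | 56.5 / 58.1% | 5.2 / 5.2% |
| 10% | 56.6 / 60.6% | 5.2 / 4.9% |
| 20% | 56.9 / 65.0% | 5.1 / 4.9% |

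Monte Carlo standard error is about 0.5 points for power and 0.2 for the error rate. The simulated gains of 0.0, 0.2, 1.6 and 4.0 points for R² from 0 to 10% agree with the formula.

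**5. Price if the covariates are useless.** At R² = 0 the simulated mean SE rises from 0.1232 to 0.1236. Power does not visibly change; by calculation the loss is at most about 0.3 points.

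**6. The same step on the plan's lognormal formula.** Power goes from 80.1% to 80.8, 81.8 and 83.6% at R² of 2, 5 and 10%. These figures describe the formula, not a count analysis with zeros.

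**The case against.** The strongest reply is that nothing here is an error. With 1:1 randomization an unadjusted comparison is not biased by omitting covariates, and the simulated error rates are the same with and without them. The plan fixes an unadjusted comparison in advance, so following it involves no after-the-fact choice. All of this stands.

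The benefit also rests on an R² the documents do not give. Enrolment excludes polyposis syndromes, HNPCC, prior colon resection and referral for a known polyp, and one operator does every procedure. These restrictions bear on how much variation is left for the covariates to explain. At R² of 2% the gain is worth about 6 patients per arm, fewer than the roughly 10 per arm (20 in total) already added for withdrawals. This stands too: the gain cannot be promised, only bounded.

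A third reply is that the unadjusted ratio matches the endpoint definition directly. It does, but under randomization an adjusted log-link model without treatment-by-covariate interactions estimates the same ratio of means. Reporting both removes the difficulty.

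Finally, a log-link model is itself a change from the planned test. Against the stated 80% its power at 294 per arm is about 56%, and covariates recover only a few points. That drop comes from the scale of analysis and the CV, not from the covariates. It means the change of model cannot be presented as part of a free addition.

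**Conclusion.** The point holds as a cheap improvement of minor severity. The primary comparison uses none of the three collected baseline variables. Naming them would add about 0 to 2 points of power at R² of 0 to 5% and about 4 points at 10%, within the same log-link model and with false non-inferiority near 5%. These figures assume 294 per arm, CV 1.5, a one-sided 5% level, truly equal devices and, for the simulation, negative binomial counts. The 20% row is an outer bound, not an expectation.

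A reader might infer three stronger things, none of which the documents support:

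- **That the missing covariates make the primary analysis biased or invalid.** Randomization rules this out.
- **That adjustment certainly yields a worthwhile gain.** No predictive strength is given, and at R² = 0 there is none.
- **That adjustment repairs the log-of-zero problem or the low power on the ratio-of-means scale.** It does neither; both are separate questions to settle on their own.

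**What to change.** Add a short statement to Statistical Analysis & Sample Size before data are analysed:

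- The primary non-inferiority model includes age (continuous), gender and indication (screening, surveillance, diagnostic) as covariates.
- The model keeps zero counts and estimates the ratio of mean adenomas per colonoscopy, for example a log-link model with robust variance.
- Non-inferiority is concluded if the adjusted one-sided 95% lower bound for AmplifEYE / Endocuff Vision exceeds 0.80.
- The unadjusted ratio from the same model is reported alongside.

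Use only characteristics fixed before randomization; bowel preparation score and diverticulosis are observed at the procedure and should stay out. Do not add the covariates to a regression on log-transformed counts, which still fails at zero and does not target the ratio of arithmetic means.

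The covariates cost 4 degrees of freedom and an SE increase of about 0.0004 if they explain nothing. They need no new data and no change in sample size. The choice of primary model and its power of about 56% at 294 per arm need their own justification and should not be treated as settled by this addition.

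### The primary log-count t-test is undefined for patients with no adenomas, no zero rule is given, and none of seven workarounds tried keeps both the 5% level and the 80% power

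*Combined protocol and SAP*

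**What the plan says.** Under Statistical Analysis & Sample Size, the primary comparison is made "using a two-sample t-test on the log-transformed adenoma count". The same approach is extended to three other counts: "Similar analyses will be performed for the number of polyps, serrated lesions, and flat lesions per colonoscopy".

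Under Objectives, the endpoint is an arithmetic mean over everyone examined: "Adenomas per colonoscopy is calculated as the total number of adenomas detected divided by the total number of colonoscopies". The adenoma detection rate is a separate secondary endpoint, "calculated as the percentage of colonoscopies in which at least one adenoma was detected", so the plan itself foresees colonoscopies with no adenoma.

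The margin is set on mean APC. Endocuff Vision is expected to give 2.3, and an acceptable result for AmplifEYE "would be within 20% of this value or 1.84". That sentence labels the quantity ADR, but 1.84 = 0.80 × 2.3, so I read it as APC. With 294 per group, "the study will have 80% power to detect non-inferiority between the two groups", assuming a one-sided two-sample t-test with "a coefficient of variation 1.5 for both groups, and a noninferiority margin of 20" per cent. Finally, "A 5% significance level will be used for all tests".

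No section gives an added constant, a replacement value, an exclusion rule or a count model for zeros. The analysis sentence states neither the margin on the log scale nor a decision rule.

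**The concern.** The first problem needs no simulation: log(0) is undefined, so the primary test cannot be computed for all randomised patients.

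The second is that each obvious repair changes the hypothesis. When all values are positive and the arms differ by a scale factor, a log t-test against ln 0.80 does test a 20% fall in the mean. Counts with zeros are not of that kind. After a constant is added, a 20% fall in APC no longer shifts the mean log by ln 0.80. Dropping zeros removes exactly the patients in whom a device found nothing.

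The trial exists to decide whether the cheaper device can replace the other. That verdict would rest on an unstated rule that could be chosen after the data are seen.

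**Working it through.** **Inputs from the plan:** APC 2.3 and 1.84 (ratio 0.80, difference 0.46), CV 1.5, 294 per group, one-sided test, 5% level. **Assumed:** the count distribution, since the plan gives only a mean and a CV; and ln 0.80 as the log-scale margin unless stated otherwise.

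**1. The plan's own figure.** For lognormal data without zeros, σ² = ln(1 + 1.5²) = 1.179, so σ = 1.086; the margin is −ln 0.80 = 0.2231. Noncentral-t power at one-sided 5% is 0.801 with 294 per group and 0.7996 with 293. The 294 is therefore reproduced, but for strictly positive lognormal data. In a zero-free check at a true ratio of 0.80, the log t-test is sound: false non-inferiority is 0.048 (lognormal) and 0.049 (gamma).

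**2. The same 294 for a test of mean APC**, taking CV as SD/mean of the raw counts:

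- Ratio: SE = √(2 × 2.25/294) = 0.1237; power = Φ(0.2231/0.1237 − 1.645) = 0.563.
- Difference: SD = 1.5 × 2.3 = 3.45; SE = 3.45 × √(2/294) = 0.2845; power = Φ(0.46/0.2845 − 1.645) = 0.489.
- CV at which the ratio test reaches 80%: √(294 × 0.2231²/(2 × 2.4865²)) = 1.088. Power by CV: 1.0, 0.856; 1.2, 0.729; 1.3, 0.669; 1.5, 0.563.

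**3. Share of zeros.** Negative binomial: variance = 3.45² = 11.90; k = 2.3²/(11.90 − 2.3) = 0.551; P(0) = (k/(k + 2.3))^k = 0.404. A Poisson-lognormal with the same mean and CV gives 0.303. A negative binomial with CV 1.09 (k = 1.327) gives 0.263.

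**4. Zero rules**, 20,000 simulated trials per scenario. NI error is the percentage of trials declaring non-inferiority at a true APC ratio of 0.80; its range covers same dispersion (or σ) and same CV in the lower arm. Power is at equal APC. All entries are percentages.

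| Rule | NB, CV 1.5: NI error | Power | Poisson-lognormal, CV 1.5: NI error | Power | NB, CV 1.09: NI error | Power |
|---|---|---|---|---|---|---|
| log(x+1) | 55.9–61.6 | 94.9 | 53.1–56.2 | 97.4 | 50.0–59.8 | 98.6 |
| log(x+1), margin ln(2.84/3.30) | 17.0–20.8 | 70.8 | 12.8–14.3 | 78.3 | 9.9–15.2 | 81.8 |
| zeros set to 1 | 58.8–60.9 | 95.6 | 56.3–57.9 | 97.2 | 48.5–51.2 | 98.3 |
| log(x+0.5) | 27.4–33.1 | 80.2 | 21.2–24.4 | 86.8 | 18.3–28.2 | 89.3 |
| zeros dropped | 29.2–33.6 | 80.2 | 43.0–44.1 | 89.4 | 34.2–41.4 | 94.6 |
| log(x+0.1) | 6.9–10.1 | 45.3 | 3.7–4.5 | 51.6 | 2.9–6.7 | 54.3 |
| log(x+0.01) | 2.4–4.1 | 23.9 | 1.1–1.3 | 27.0 | 0.9–2.6 | 28.7 |
| *APC ratio, robust SE* | 5.1–5.2 | 55.8 | 5.3–5.6 | 58.4 | 4.8–5.1 | 80.0 |

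A mean-scale contrast, mean(AmplifEYE) − 0.8 × mean(Endocuff Vision), gives 4.9–5.0% error and 55.2% power in the first setting.

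**5. Why the rules fail** (negative binomial, CV 1.5, same dispersion). When APC falls by 20%, the mean of log(x+1) falls by only 0.105, well inside both 0.2231 and the translated −ln(2.84/3.30) = 0.150. With SD 0.823, SE = 0.823 × √(2/294) = 0.0679, and Φ((0.2231 − 0.105)/0.0679 − 1.645) is about 0.54, close to the simulated 56% (this uses the control-arm SD for both arms). With log(x+0.01) the fall is 0.295, beyond the margin, but the SD rises to 2.82 against the planned 1.086. Then SE = 0.233 and power = Φ(0.2231/0.233 − 1.645), about 0.25.

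**The case against.** Six points can be made for the other side; none supplies the missing rule.

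- **The benchmark mixes two problems.** At CV 1.5 the direct APC-ratio test also misses 80% power, at about 56%. This stands: the power shortfall is not due to zeros alone but also to sizing on a lognormal formula. The ratio test does, however, hold the level for the quantity the margin is set on. At CV 1.09 it reaches 80% while still no listed rule gives both figures.
- **The largest error rates depend on a margin the plan does not state.** Translating the log(x+1) margin cuts the error from 56–62% to 17–21%. Translated margins give 13–17% error with 65% power for log(x+0.5), and 6–9% with 43% for log(x+0.1). Calibrating the log(x+1) margin to the assumed null distribution gives about 5–6% and 46%. So the extreme figures soften, but the level is then either still exceeded or bought with a large loss of power.
- **The distribution is assumed.** True, and the percentages are illustrations, not properties of this trial. The undefined log and the absent rule depend on no assumption.
- **Sidedness is not settled.** Only the power sentence says one-sided, and I follow it. At one-sided 2.5% the ratio test would have about 44% power at CV 1.5 and 70% at CV 1.09.
- **Pre-specifying a zero rule would cure the undefined test.** It would, but the rule would still not test a 20% difference in mean APC.
- **Restating power is disclosure, not repair.** At CV 1.5, 80% power for the ratio test would need 4.5 × (2.4865/0.2231)² ≈ 559 per group. This is fair as a measure of the gap. The analysis can nevertheless be corrected without enlarging the trial.

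**Conclusion.** The concern holds and must be fixed. The primary test cannot be computed for patients with no adenomas, whom the plan expects, and nothing elsewhere in the document supplies a rule.

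Its size can only be illustrated. At the plan's mean and CV, under the negative binomial assumption, false non-inferiority across the seven rules ranges from about 2% to 62%, and power from 24% to 96%. No rule delivered both stated figures under any of the three count models. The exact percentages rest on those models, one-sided 5%, 294 per group and, except for the translated row, ln 0.80 as the margin. The arithmetic behind 294 is correct for zero-free lognormal data, which adenoma counts are not.

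**What to change.** Replace the log-count t-test sentence under Statistical Analysis & Sample Size with:

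> The APC ratio (AmplifEYE/Endocuff Vision) will be estimated from untransformed counts, including all patients with zero adenomas, using a log-link count model with robust standard errors. Non-inferiority is declared if the one-sided 95% lower confidence limit exceeds 0.80. Polyp, serrated-lesion and flat-lesion counts will be analysed with the same model.

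The mean-scale contrast described above would also serve.

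Replace the power sentence with:

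> With 294 patients per group and a raw-count CV (SD/mean) of 1.5 in both groups, this analysis has about 56% power at equal APC; power is about 73% at a CV of 1.2 and 80% at a CV of about 1.09.

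The cost is two sentences, with standard software and no new data items, visits or patients; 294 per group can stay. The drawback is that stated power falls from 80% to about 56% if CV 1.5 describes the raw counts. The sponsor would have to say so openly, or show from its source data that the raw-count CV is about 1.09 or lower.

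### Does a chi-square test without an exact fallback give misleading results for rare complications, failed sigmoid passage and failed cecal intubation?

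*Combined protocol and SAP*

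**What the plan says.** The Objectives section lists "Complications encountered during procedure (i.e., mucosal trauma, perforation, or gastrointestinal bleeding") among the secondary endpoints, together with success in passing the device through the sigmoid colon and the cecal intubation rate. Statistical Analysis & Sample Size assigns one method to all of them: "Chi-square tests will be used to compare the groups for differences in adenoma, polyp, serrated lesion, and flat lesion detection rates; complications", and, in the same sentence, "ability to pass the device through the sigmoid colon; and cecal intubation rate". The level is also fixed: "A 5% significance level will be used for all tests".

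The section does not say whether the chi-square test carries a continuity correction. It gives no exact test, no rule for small expected counts and no confidence interval for these endpoints. For exam times, by contrast, it does name a rank-based alternative. Neither the protocol nor the analysis section gives an expected frequency for any complication, for failed passage or for failed intubation.

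**The concern.** The usual textbook caution is that the chi-square approximation becomes doubtful when an expected cell count is below 5. Perforation and bleeding that needs intervention could well be that rare, and failed intubation might be too, since patients referred after an incomplete colonoscopy are excluded. If four events fell in one arm and none in the other, the uncorrected test would be significant at 5% and Fisher's test would not. The trial asks whether a cheaper device can replace another, so a spurious safety signal would matter. So would a non-significant result that is read as proof of equal safety. The rank-test fallback for exam times makes the lack of one here look like an oversight.

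**Working it through.** **Inputs.** 294 per group (Statistical Analysis & Sample Size: "With a sample size of 294 patients per group, the study will have 80% power to detect non-inferiority between the two groups"), 1:1 allocation (Randomization), and a 5% level. The documents give no event rates, so a range is assumed below.

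**The plan's own figure.** The 294 is reproduced on the log scale:
- SD = √ln(1 + 1.5²) = 1.0857; margin = −ln 0.8 = 0.2231; one-sided 5%; 80% power.
- Normal approximation: 2 × (1.645 + 0.842)² × 1.0857² / 0.2231² ≈ 293.
- The noncentral t gives 294 (power 0.8007).

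This sets the arm size. The sample size was not derived from the binary endpoints.

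**When expected counts fall below 5.** With T events in 588 patients, the expected count per arm is T/2. This is below 5 when T < 10, that is, below 10/588 = 1.7%.

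**The four-against-none table.**
- Uncorrected: X² = 588 × (4 × 294)² / (294 × 294 × 4 × 584) = 4.03, p = 0.045.
- With Yates' correction: X² = 588 × (1176 − 294)² / (294 × 294 × 4 × 584) = 2.27, p = 0.132.
- Fisher: 2 × C(294,4)/C(588,4) = 0.124.
- Other exact tests: Barnard 0.046, Boschloo 0.108.

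The 20 extra patients change nothing: at 304 per arm the uncorrected and Fisher p-values are again 0.045 and 0.124. So 0.124 is one exact p-value among several, and Barnard's agrees with the uncorrected chi-square.

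**True error rate.** For a common event rate π, sum Bin(i; 294, π) × Bin(j; 294, π) over all tables (i, j) that the test rejects at 5%:

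| Assumed rate | Chance of T < 10 | Uncorrected chi-square | Fisher |
|---|---|---|---|
| 0.2% | >99.9% | 0.003 | <0.001 |
| 0.5% | 99.9% | 0.029 | 0.002 |
| 1% | 92.5% | 0.046 | 0.012 |
| 1.5% | 61% | 0.046 | 0.019 |
| 1.7% | 46% | 0.047 | 0.021 |
| 2% | 26% | 0.049 | 0.023 |
| 3% | 1.7% | 0.051 | 0.028 |

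The largest value for the uncorrected test at rates up to 5% is 0.051, near 2.6%.

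**Why 12% and under 5% are both right.** Given exactly four events, all four fall in one arm with probability 0.124. But four events must first occur. At a rate of 0.75%, that has probability 0.192, so the four-against-none table has probability 0.192 × 0.124 = 0.024. Totals of three or fewer never reach significance (three against none gives p = 0.082). Over all totals, the error rate at 0.75% is 0.043.

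**The case for a change.** The strongest reply is that an analyst reports the table actually seen, not an average over tables. Given four events, a split this extreme arises by chance 12% of the time, and p = 0.045 does not convey that. This is a coherent conditional argument, but it expresses a preference between two accepted modes of inference. The unconditional error rate is held, so the planned test is not invalid.

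A second reply is that the unnamed variant lets the analyst choose after seeing the data: four against none gives 0.045 or 0.132, and five against none gives 0.025 or 0.072. The omission is real. Its effect is bounded, because Yates' correction can only lower the statistic. Every table significant with it is also significant without it, so even a choice made after the fact cannot push the error rate above that of the uncorrected test.

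A third reply is that a bare p-value does not show how much harm remains possible. That is true: with 0 of 294 events, the exact 95% upper limit is 1 − 0.025^(1/294) = 1.25%. But this holds for any test, and a switch to Fisher would not help. Five against none would move from p = 0.025 to 0.061, so a real difference would be harder to flag and more results could be misread as equal safety. Intervals would be a sensible reporting addition. They are a separate matter from whether the chi-square test is wrong.

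**Conclusion.** The concern is not upheld. Followed as written, the plan gives valid tests of these endpoints. The uncorrected chi-square keeps its true error rate at or below 0.047 for event rates up to 1.7% and at about 0.051 at most for rates up to 5%. With Yates' correction the test is stricter still. The four-against-none example needs the uncorrected variant, which the plan does not specify. Frequent sparse tables need rates of roughly 1.5% or lower, which the documents do not state. The complications endpoint also includes mucosal trauma, whose frequency is not given and which may not be rare.

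The consequence is limited too. The Background section rests the replacement argument on adenomas per colonoscopy, and no decision rule uses the complication, passage or intubation p-values. The primary analysis and the sample size are untouched. What remains is unspecified detail: the variant, a rule for sparse tables, and interval estimates. The conclusion assumes two arms of about 294, independent patients and a common event rate under the null hypothesis.
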